•	To determine whether cotadutide is superior to placebo on resolution of NASH without worsening of liver fibrosis in participants with non-cirrhotic NASH with fibrosis	•	Proportion of participants with resolution of NASH without worsening of liver fibrosis based on biopsy at Week 48
•	To assess the effect of cotadutide versus placebo on improvement in fibrosis by at least one stage without worsening of NASH	•	Proportion of participants with improvement of liver fibrosis by at least one stage without worsening of NASH based on biopsy at Week 48
•	To assess the effect of cotadutide versus placebo on resolution of NASH and improvement in fibrosis	•	Proportion of participants with both resolution of NASH and improvement in fibrosis by at least one stage based on biopsy at Week 48
•	To assess the effect of cotadutide versus placebo on improvement in fibrosis by at least one stage	•	Proportion of participants with improvement in fibrosis by at least one stage based on biopsy at Week 48
•	To assess the effect of cotadutide versus placebo on improvement in NAS	•	Proportion of participants with improvement in NAS based on biopsy at Week 48 Change from baseline in NAS based on biopsy at Week 48
•	To assess the effect of cotadutide versus placebo on change in fibrosis	•	Change from baseline in fibrosis stage based on biopsy at Week 48 Proportion of participants with progression, no change, or regression in fibrosis stage based on biopsy at Week 48
•	To assess the effect of cotadutide versus placebo on improvement in each key histological feature of NASH	•	Proportion of participants with improvement in key histological features of NASH based on biopsy at Week 48, including:  Inflammation  Steatosis  Ballooning
•	To characterize using AI-based histology assessment the effect of cotadutide versus placebo on NASH histology, including:  Resolution of NASH without worsening of liver fibrosis	•	AI-based histology assessment of:  ° Proportion of participants with resolution of NASH without worsening of liver fibrosis based on biopsy at Week 48

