•	To assess the effect of cotadutide versus placebo on improvement in NAS	
 
Proportion of participants with improvement in NAS based on biopsy at Week 48
 
Change from baseline in NAS based on biopsy at Week 48
 

•	To assess the effect of cotadutide versus placebo on change in fibrosis	
 
Change from baseline in fibrosis stage based on biopsy at Week 48
 
Proportion of participants with progression, no change, or regression in fibrosis stage based on biopsy at Week 48
 

•	To assess the effect of cotadutide versus placebo on improvement in each key histological feature of NASH	Proportion of participants with improvement in key histological features of NASH based on biopsy at Week 48, including:  Inflammation Steatosis Ballooning
•	To characterize using AI-based histology assessment the effect of cotadutide versus placebo on NASH histology, including:  Resolution of NASH without worsening of liver fibrosis  Improvement of liver fibrosis by at least one stage without worsening of NASH  Resolution of NASH and improvement in fibrosis  Improvement in fibrosis by at least one stage  Improvement in NAS  Change in fibrosis  Improvement in each key histological feature of NASH	
 
AI-based histology assessment of:         
 
Proportion of participants with resolution of NASH without worsening of liver fibrosis based on biopsy at Week 48
 
Proportion of participants with improvement of liver fibrosis by at least one stage without worsening of NASH based on biopsy at Week 48
 
Proportion of participants with both resolution of NASH and improvement in fibrosis by at least one stage based on biopsy at Week 48
 
Proportion of participants with improvement in fibrosis by at least one stage based on biopsy at Week 48
 
Proportion of participants with improvement in NAS based on biopsy at Week 48
 
Change from baseline in NAS based on biopsy at Week 48
 
Change from baseline in fibrosis stage based on biopsy at Week 48
 
Proportion of participants with progression, no change, or regression in fibrosis stage based on biopsy at Week 48
 
Proportion of participants with progression, no change, or regression in fibrosis stage based on biopsy at Week 48
 
Proportion of participants with improvement in histological features of NASH based on biopsy at Week 48, including:

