•	To assess the effect of cotadutide versus placebo on circulating markers of hepatic inflammation	•	Change from baseline in liver enzymes including ALT and AST through Week 48
•	To assess the effect of cotadutide versus placebo on lipid profile and glycemic control	•	Change from baseline in triglycerides, LDL cholesterol, HDL cholesterol, non-HDL cholesterol, total cholesterol, and HbA1c through Week 48
•	To summarize the PK profile of cotadutide	•	Cotadutide PK exposure will be summarized and compared with prior data for consistency
•	To assess the effect of cotadutide versus placebo on liver stiffness	•	Change from baseline at Week 48 in:  LSM as assessed by FibroScan  Percentage CAP as assessed by FibroScan
•	To assess the effect of cotadutide versus placebo on disease-specific biomarkers	•	Changes from baseline at Week 48 in non-invasive disease-specific biomarkers, including but not limited to:  Collagen turnover (Pro-C3)  FIB-4  APRI  NFS  BARD score  FAST score  Agile 3+
•	To determine whether cotadutide is superior to placebo for weight reduction	•	Percent change from baseline in body weight at Week 48
•	To assess the effect of cotadutide versus placebo on glucose, adiponectin, and C-peptide	•	Change from baseline in fasting plasma glucose, adiponectin, and C-peptide at Week 48
•	To determine whether treatment with cotadutide compared with placebo will result in a reduction of BP	•	Change from baseline in SBP through Week 48

Resolution of NASH is defined as the absence of fatty liver disease or isolated simple steatosis without steatohepatitis and a NAS ballooning score of 0, inflammation score of 0 to 1, and steatosis score of any degree (from 0 to 3), as assessed by NASH Clinical Research Network/NAS score.

Improvement in fibrosis is defined as a one or more category improvement in the fibrosis category (NASH Clinical Research Network fibrosis stage) without worsening of NASH.

Worsening of NASH is defined as any increase in the ballooning, inflammation, or steatosis scores even if total NAS does not increase.

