#### 4 STUDY DESIGN

# 4.1 Overall Design

This study was originally designed as a 2-part, Phase IIb/III, global, randomized, parallel-group, double-blind, placebo-controlled, multicenter, proof of concept study to assess the safety and efficacy of 300 and 600 µg cotadutide compared with placebo, given once daily as an SC injection administered via a multidose pen, in adults with non-cirrhotic NASH with fibrosis stage F2 or F3. After carefully considering several factors, foremost being the identification of other, more convenient treatments for patients with NASH, the sponsor made a strategic decision to discontinue development of cotadutide and recruitment into this study. Randomized participants and participants in active screening will be allowed to continue participation. Given the reduced sample size, the primary goal of this study is to evaluate the safety and tolerability of cotadutide in participants with non-cirrhotic NASH with fibrosis. The Phase III portion of the study (Part B) will not be conducted.

Part A (Phase II) will assess the safety and efficacy of 300  $\mu$ g and 600  $\mu$ g cotadutide treatment.

Participants will be  $\geq 18$  to  $\leq 75$  years of age (inclusive) with biopsy-proven NASH (historical biopsy performed  $\leq 180$  days from randomization or on-study biopsy) demonstrating a NAS  $\geq 4$  (with a score of at least 1 for each component: steatosis, lobular inflammation, and ballooning) and liver fibrosis stage F2 or F3. Approximately 600 participants will be screened/enrolled in the study (in approximately 20 countries) to achieve approximately 55 randomly assigned to study intervention.

At randomization, participants will be stratified by the presence/absence of T2DM and by fibrosis stage (Section 6.3.1). Participants will undergo dose titration steps every 4 weeks to reach the target dose of 300 µg or 600 µg qd. Dose titration will start from 50 µg cotadutide (or matching placebo) qd and increase to 100 µg qd after 4 weeks, and then increase by 100-µg increments every 4 weeks, until reaching the final intended dose at Week 12 for the 300 µg treatment groups and Week 24 for the 600 µg treatment groups. To mitigate the risk of gastrointestinal AEs, it is important to follow the 4-week dose escalation intervals (refer to Section 6.6 for dose modifications). Each cotadutide treatment group will be placebo-matched with respect to titration schedule and dose levels.

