## 4.2.3 Other Endpoints

#### 4.2.3.1 Definition

Tertiary/exploratory endpoints will be tested versus placebo at the 2-sided nominal alpha 5% level, without consideration of multiplicity:

The following are histological endpoints, to be assessed centrally 1) by independent pathologists and 2) by artificial intelligence, as detailed in the Central Histopathology Review

Charter. Analysis of continuous histological scores, if included, will be based solely on values provided by artificial intelligence.

- Proportion of participants with resolution of NASH without worsening of liver fibrosis based on biopsy at Week 48
- Proportion of participants with improvement of liver fibrosis by at least 1 stage without worsening of NASH based on biopsy at Week 48. (Worsening of NASH is defined as any increase in the ballooning, inflammation, or steatosis scores even if total NAS does not increase.)
- Proportion of participants with both resolution of NASH and improvement in fibrosis by at least 1 stage based on biopsy at Week 48
- Proportion of participants with improvement in fibrosis by at least 1 stage based on biopsy at Week 48
- Proportion of participants with improvement in NAS based on biopsy at Week 48
- Change from baseline in NAS based on biopsy at Week 48
- Change from baseline in fibrosis stage based on biopsy at Week 48
- Proportion of participants with progression, no change, or regression in fibrosis stage based on biopsy at Week 48
- Proportion of participants with improvement in key histological features of NASH on biopsy at Week 48, including:
  - Inflammation
  - Steatosis
  - Ballooning

Below are other exploratory/tertiary endpoints not based on biopsy:

- Change from baseline in liver enzymes including ALT and AST through Week 48
- Change from baseline in triglycerides, LDL cholesterol, and HDL cholesterol, non-HDL cholesterol, and total cholesterol, and HbA1c through Week 48
- Cotadutide PK exposure will be summarized and compared with prior data for consistency
- Change from baseline at Week 48 in:
  - LSM as assessed by FibroScan
  - Percentage CAP as assessed by FibroScan
- Changes from baseline at Week 48 in non-invasive disease-specific biomarkers, including but not limited to:
  - Pro-C3

- ELF score
- FIB-4
- APRI
- NFS
- BARD score
- FAST score
- Agile 3+
- Percent change from baseline in body weight at Week 48
- Change from baseline in FPG, adiponectin, and C-peptide at Week 48

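### The protocol's definition of fibrosis improvement includes no worsening of NASH, so the fibrosis-only and combined histology endpoints can be derived in two ways

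*Protocol*

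**What the plan says.** Table 8 in Protocol 3.1 lists three binary Week 48 biopsy endpoints that use fibrosis improvement:

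- **A**, which names the NASH condition: "Proportion of participants with improvement of liver fibrosis by at least one stage without worsening of NASH based on biopsy at Week 48".
- **B**, which does not: "Proportion of participants with improvement in fibrosis by at least one stage based on biopsy at Week 48" (this wording is also in synopsis Table 1).
- **C**, the combined endpoint: "Proportion of participants with both resolution of NASH and improvement in fibrosis by at least one stage based on biopsy at Week 48".

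Table 8 repeats all three for the AI-based reads, and Protocol 9.4.2 lists A, B and C as separate analyses.

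The Table 8 footnote then gives three definitions:

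- Improvement in fibrosis is "one or more category improvement in the fibrosis category (NASH Clinical Research Network fibrosis stage) without worsening of NASH". It is not limited to any one endpoint.
- "Worsening of NASH is defined as any increase in the ballooning, inflammation, or steatosis scores even if total NAS does not increase".
- Resolution requires, among other things, "a NAS ballooning score of 0, inflammation score of 0 to 1, and steatosis score of any degree (from 0 to 3").

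SAP 4.2.3.1 keeps the three endpoints separate, with B as "Proportion of participants with improvement in fibrosis by at least 1 stage based on biopsy at Week 48". It repeats the definition of worsening once, in parentheses beside A. SAP 4.2.3.2 says that fibrosis improvement is derived from the vendor's component scores and stages, but gives no rule for it. SAP Section 2 declares one departure from the protocol, the change to the per protocol set.

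**The concern.** The only definition of fibrosis improvement in either document contains the condition that is meant to distinguish A from B. If the definition holds, B repeats A and the qualifier in A does nothing. If B means stage change alone, the definition is wrong. The list of endpoints and the definition cannot both stand.

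C is affected too. Its resolution half leaves steatosis unrestricted, but the footnote brings in a steatosis restriction through the fibrosis half.

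At stake is whether B and C are reproducible. Two programmers, each following the documents, could report different responder counts for the same data, on both the pathologist and the AI reads.

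**Working it through.** The plan has no figure to reproduce here, so the check is logical. Let S = fibrosis stage falls by at least one; W = any rise in ballooning, inflammation or steatosis; R = resolution of NASH.

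| Endpoint | Footnote applied | Stage change only |
|---|---|---|
| A | S and not W | S and not W |
| B | S and not W | S |
| C | R and S and not W | R and S |

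**Inputs.** Entry requires F2 or F3 and a NAS of at least 4, "with a score of at least 1 for each component: steatosis, lobular inflammation, and ballooning" (Protocol 4.1). The steatosis range 0 to 3 is in the Table 8 footnote. The ranges for inflammation (0 to 3), ballooning (0 to 2) and fibrosis (0 to 4) are assumptions; they affect the counts below but not the logic.

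**Possible score pairs**
- Baseline component sets: 3 × 3 × 2 = 18, less the one set with NAS 3, = 17. With two stages: 34 baseline states.
- Post-baseline states: 4 × 4 × 3 × 5 = 240. Pairs: 34 × 240 = 8,160.
- Lower stages available: 2 from F2 and 3 from F3, 5 in all.

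**A against B**
- B, stage only: 17 × (4 × 4 × 3) × 5 = 4,080 pairs.
- A: the post-baseline sets with no component rise number (s+1)(i+1)(b+1) for each baseline set. The sum over the 17 sets is 9 × 9 × 5 − 8 = 397, and 397 × 5 = 1,985 pairs.
- Under the footnote, B is also met in the same 1,985 pairs, so A and B agree in all 8,160. With stage change only, they differ in 4,080 − 1,985 = 2,095.

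**C**
- Resolved component sets: 4 × 2 × 1 = 8. Stage only: 17 × 8 × 5 = 680 pairs.
- With the footnote: 5, 6 and 6 baseline sets have steatosis 1, 2 and 3, and allow 2, 3 and 4 post-baseline steatosis scores. (5×2 + 6×3 + 6×4) × 2 × 5 = 520 pairs.
- The footnote removes 680 − 520 = 160 pairs, all through steatosis rising from 1 or 2. Ballooning must reach 0 and inflammation 0 or 1, both from baselines of at least 1, so neither can worsen in a resolved participant.
- Example: baseline steatosis 1, inflammation 1, ballooning 2, F2; Week 48 steatosis 2, inflammation 1, ballooning 0, F1. This participant meets C on stage change and fails it under the footnote.

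These are counts of possible score combinations, not expected patient frequencies.

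**An unevaluable steatosis score.** SAP 4.2.3.2 still concludes resolution when steatosis cannot be scored. Under the footnote, C could not be confirmed for that participant, because absence of a steatosis increase cannot be shown.

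**Size.** About 55 participants are randomized 2:1:2:1, so each dose group and pooled placebo has about 55 × 2/6 = 18.3. One reclassified participant moves a rate by 1/18.3 = 5.5 percentage points. As an illustration only: suppose the stage-improvement rate is 30% and 10% to 30% of those participants also have a component rise. B under the footnote is then 0.30 × 0.9 = 27% to 0.30 × 0.7 = 21%. With 0.30 × 18.3 = 5.5 responders per group, that is 0.5 to 1.6 participants. Neither input is in the documents.

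**The case against.** The case for a stage-only reading is good. B is worded so that it needs no definition. The SAP attaches the worsening definition only to A. Protocol 9.4.2 lists A and B separately, and Protocol 9.4 leaves technical detail to the SAP. The footnote reading makes one endpoint redundant, so a sensible programmer would probably use stage change. This stands as evidence of intent, but it does not override a definition that the SAP neither replaces nor lists as changed.

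A reader might infer that pure fibrosis improvement goes unmeasured, or that its rate will be biased low. The documents do not support either:

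- Both list the proportions with progression, no change or regression in stage, and SAP 4.2.3.4 adds shift tables of stage by treatment. Regression carries no NASH condition. It is not a full substitute for B, because under SAP 4.2.3.3 ordinal endpoints are not imputed, whereas binary biopsy endpoints on the FAS count missing biopsies as non-responders.
- The lower rate arises only if the footnote is followed, and it is then the rate of a stricter endpoint. No bias in the treatment difference has been shown.

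The effect on C is narrow: it needs resolved NASH, a better fibrosis stage and a rise in steatosis together. Nothing in the documents says how often that happens.

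**Conclusion.** The inconsistency is real. Applied as written, the Table 8 footnote makes B identical to A and adds a no-increase-in-steatosis condition to C. The surrounding text suggests that this was not intended, but does not rule it out, so B and C can each be programmed in two ways. The direction is certain: the footnote reading gives equal or lower responder rates. The size is unknown, because the documents give no frequency of component worsening among participants whose stage improves; the 21% to 27% illustration rests wholly on assumed inputs.

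The consequence is limited. Safety is primary, and all the affected endpoints are exploratory with nominal p-values. The histology estimand in Protocol 3.3 concerns resolution without worsening of fibrosis. The subgroup analyses in SAP 4.2.3.6 use that endpoint and A, not B or C. No primary conclusion changes. It should still be settled before unblinding, since either choice made afterwards could be questioned.

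**What to change.** Add a rule to SAP 4.2.3.2, for both pathologist and AI reads: improvement in fibrosis means a decrease of at least one stage from the baseline eligibility read (SAP 3.3.1.1), and the no-worsening-of-NASH condition applies only to the endpoint that names it. B is then stage change alone, and C is resolution plus stage change with steatosis unrestricted.

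Record this in SAP Section 2 as a departure from the Table 8 footnote, and correct the footnote at any next protocol amendment. An amendment for this alone is not warranted, because Protocol Appendix A 1 requires ethics and regulatory approval for amendments. The cost is one derivation rule and one entry in Section 2, with no new data or analyses.

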# 3.2 Objectives and Endpoints: Part B

Due to the decision to end recruitment into the study, Part B of the study will not be

conducted.

#### 3.3 Estimands

The primary clinical questions of interest are:

#### Part A

In patients with non-cirrhotic NASH with liver fibrosis with a treatment strategy to titrate to a maximum dose of 300 or 600 µg cotadutide versus placebo, what is the difference in proportion achieving **resolution of NASH without worsening of liver fibrosis at Week 48** in patients regardless of treatment discontinuation, deviations from the protocol titration schedule, changes in background medication, liver events, or use of prohibited medication or other protocol deviations.

The primary estimands are described by the following attributes:

**Population**: Patients with non-cirrhotic NASH with liver fibrosis (F2 or F3), with or without T2DM.

**Endpoints**: Resolution of NASH without worsening of liver fibrosis at Week 48

Treatment condition: Treatment strategy to titrate to a maximum dose of 300 μg or 600 μg cotadutide or matching placebo. The planned titration schedule is described in Section 4.1, and possible modifications to the titration schedule are described in Section 6.6. Permitted concomitant medications are described in Section 6.5.1, and restricted or prohibited concomitant medications are described in Section 6.5.2.

Treatment Policy Strategy: If a biopsy is obtained within the analysis window, the
endpoint will be defined based on the observed biopsy result regardless of the occurrence
of intercurrent events of treatment discontinuation, deviations from the protocol titration
schedule, changes in background medication, liver event, or use of prohibited medications
or other protocol deviations.

Population-level summary: Difference in proportion of responders

**Rationale for estimand**: The endpoints and intercurrent event strategies for the primary estimands are aligned to current regulatory guidance for investigation of non-cirrhotic NASH therapies.

#### 4 STUDY DESIGN

# 4.1 Overall Design

This study was originally designed as a 2-part, Phase IIb/III, global, randomized, parallel-group, double-blind, placebo-controlled, multicenter, proof of concept study to assess the safety and efficacy of 300 and 600 µg cotadutide compared with placebo, given once daily as an SC injection administered via a multidose pen, in adults with non-cirrhotic NASH with fibrosis stage F2 or F3. After carefully considering several factors, foremost being the identification of other, more convenient treatments for patients with NASH, the sponsor made a strategic decision to discontinue development of cotadutide and recruitment into this study. Randomized participants and participants in active screening will be allowed to continue participation. Given the reduced sample size, the primary goal of this study is to evaluate the safety and tolerability of cotadutide in participants with non-cirrhotic NASH with fibrosis. The Phase III portion of the study (Part B) will not be conducted.

Part A (Phase II) will assess the safety and efficacy of 300  $\mu$ g and 600  $\mu$ g cotadutide treatment.

Participants will be  $\geq 18$  to  $\leq 75$  years of age (inclusive) with biopsy-proven NASH (historical biopsy performed  $\leq 180$  days from randomization or on-study biopsy) demonstrating a NAS  $\geq 4$  (with a score of at least 1 for each component: steatosis, lobular inflammation, and ballooning) and liver fibrosis stage F2 or F3. Approximately 600 participants will be screened/enrolled in the study (in approximately 20 countries) to achieve approximately 55 randomly assigned to study intervention.

At randomization, participants will be stratified by the presence/absence of T2DM and by fibrosis stage (Section 6.3.1). Participants will undergo dose titration steps every 4 weeks to reach the target dose of 300 µg or 600 µg qd. Dose titration will start from 50 µg cotadutide (or matching placebo) qd and increase to 100 µg qd after 4 weeks, and then increase by 100-µg increments every 4 weeks, until reaching the final intended dose at Week 12 for the 300 µg treatment groups and Week 24 for the 600 µg treatment groups. To mitigate the risk of gastrointestinal AEs, it is important to follow the 4-week dose escalation intervals (refer to Section 6.6 for dose modifications). Each cotadutide treatment group will be placebo-matched with respect to titration schedule and dose levels.

An independent DMC will be established to monitor data on an ongoing basis to ensure safety of participants enrolled in this study (Section 9.6).

Figure 1 (Section 1.1) is an overview of the study design. Details on treatments given during the study are presented in Section 6. Details on what is included in the efficacy and safety endpoints are presented in Section 3.

